2.2.4 Study Schedule

Schedule of Activities (SOA)

Measurement/Procedure	Primary Phase Through 36 Weeks PMA				Post-36 Weeks Visit	Follow-Up Period (≤ 12 Months Corr. Age)
	Screening	Primary Period (Days 1-3)	Extended Period (Days 4-7)	Final Period (Day 8 to Final Visit ¹)		
Informed Consent	X					
Inclusion/Exclusion Criteria	X					
Demographics	X					
Maternal/Birth/Medical Hx	X					
Chest Radiograph ²	X	X	X			
Respiratory support	X	X	X	X		X
Physical Examination	X			X		
Randomization		X				
Study Treatment Admin.		X				
Technical Perform. of Device		X				
PCO ₂		X ^{3,4}				
FiO ₂ , SpO ₂ , Vital Signs, PEEP		X ^{3,4}	X ⁵			
Respiratory ventilation/support				X	X	X
AEs and ADEs		X	X	X		
Concomitant Medication		X	X	X	X ⁶	X ⁶
Complications of Prematurity				X		
Final Visit/Discharge				X	X ⁷	
Hosp. and Emerg. Visits Info.					X	X
Health Assessment						X
Abbrev. PE, Neuro. Exam						X ⁸
Growth Assessment						X ⁸

Note: Day 1 for all subjects is the day of the initial study treatment.

¹ 36 weeks PMA, hospital transfer, or hospital discharge (whichever occurs first). Subjects must remain in the study until 28 days of life, unless transferred/discharged or death.

² A chest radiograph must be obtained prior to dosing to confirm RDS diagnosis and absence of air leak. An additional chest radiograph is required prior to any intubation if such a procedure does not delay or compromise the emergent care of the subject.

³ Documented at randomization, every 30 minutes after randomization until initiation of study treatment.

⁴ Study Days 1-3: time 0 (study treatment initiation), 10, 20, 30, 40, 50, 60, 70, 80, 90, 100, 110, 120, 130, 140, 150 minutes (\pm 3 minutes) after initiation (through 70 minutes for repeat treatments); 3 ± 0.5 , 6 ± 1 , 9 ± 1 , 12 ± 1 , 18 ± 2 , 24 ± 2 , 36 ± 2 , 48 ± 2 , 60 ± 2 and 72 ± 2 hours after initiation.

⁵ Recorded at 08:00 and 20:00 daily through Day 7.

⁶ Bronchodilators, steroids, and palivizumab (Synagis) use only.

⁷ If discharge occurs after 36 weeks PMA.

⁸ 12-months corrected age only.

3 STUDY SUBJECT CHARACTERISTICS

3.1 Subject Disposition

Subject disposition will be summarized by treatment group using frequency and percent. The number of subjects screened and randomized will be described.

The number of subjects who completed the study or died will be summarized using frequency and percent by treatment group and overall. Reasons for early discontinuation from the study include withdrawal of consent and lost-to-follow up. A subject may withdraw consent (through their legally authorized guardian) at any time without prejudice to further care.

The number of subjects who discontinued treatment early will be summarized using frequency and percent by treatment group and overall. Reasons for early discontinuation of treatment include device failure or malfunction, AE or ADE during dosing, PI's best medical judgment, and respiratory deterioration during dosing.

3.2 Demographics and Baseline Characteristics

3.2.1 Demographics

Continuous variables (eg, gestational age, birth weight) will be summarized using mean, standard deviation (SD), median, minimum, and maximum. Categorical variables (eg, sex, race, ethnicity) will be summarized by treatment group using frequency and percent.

3.2.2 Medical, Birth and Maternal History

The mode of delivery (vaginal, c-section), type of birth (single, multiple), and incidence of congenital anomalies will be summarized by treatment group using frequency and percent. The Apgar score at 1 and 5 minutes and antenatal steroid use will be summarized by treatment group using mean, SD, median, minimum, and maximum.

Incidence of medical history findings, incidence and type of ruptured membranes, incidence of clinical chorioamnionitis, and the incidence and number of doses of antenatal steroids will be summarized by treatment group using frequency and percent.

3.3 Study and Concomitant Medication

3.3.1 Compliance

Percent compliance for this study is not applicable as all subjects will be administered at least one dose by study staff in the NICU. The number of subjects who experienced treatment interruptions for the initial or repeat doses will be summarized by treatment group.

3.3.2 Number of Doses

The number of doses (initial and repeat study treatments) received by subjects and the number of times a subject qualified for a repeat dose will be summarized by treatment group.

3.3.3 Previous and Concomitant Medication

Medications taken since birth and concomitant medications will be coded according to the World Health Organization (WHO) drug dictionary. Medications will be summarized using frequency and percentages for each treatment group by drug category and generic name.

3.4 Protocol Violations/Deviations

A protocol violation occurs when the PI fails to adhere to any significant protocol requirement affecting the inclusion, exclusion, subject safety, and primary endpoint criteria. A protocol deviation is any deviation from the protocol that does not rise to the level of a protocol violation. All protocol violations/deviations will be summarized by treatment group and listed by subject.

4 EFFICACY ANALYSIS

The efficacy objective is to assess the size of the clinical effect of lucinactant for inhalation in comparison to nCPAP alone, as demonstrated by the occurrence of and time to respiratory failure due to RDS or all-cause death through 72 hours and 28 days, BPD and related severity at 36 weeks PMA, incidence rate of survival without BPD at 36 weeks PMA, oxygen saturation and use of supplemental oxygen, common complications of prematurity, duration of MV and oxygen requirement, physiologic parameters (FiO₂, PCO₂, and SpO₂), and number/ duration of re-hospitalizationb and urgent care visits. In addition, the study will evaluate the device performance and the ability to administer up to 3 lucinactant for inhalation repeat treatments.

Given that only 12 subjects were enrolled prior to study termination, hypothesis testing will not be done and statistical tests will not be performed.

4.1 Efficacy Populations

For efficacy analyses, subjects will be summarized according to their assigned (randomized) treatment. The subjects enrolled open-label with active treatment (the first 2 subjects from each site) will not be summarized separately.

The analysis of both the primary and secondary objectives will be based on all enrolled preterm neonates (ITT population).

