The administration of study treatment may be discontinued at any time prior to the completion of dosing if certain device malfunctions or interruptions occur which cannot be corrected in a safe and timely manner or based on the clinical judgment of the PI. Reasons for discontinuation of study treatment include, but are not limited to the following:

1. A device malfunction occurs
2. The device shuts down as a result of a detected out of range condition
3. An AE or ADE which places subject at risk occurs (eg, pulmonary hemorrhage; airway obstruction)
4. If, in the PI's best medical judgment, initiating or continuing the subject's exposure to study treatment is not in the best interest of the subject's safety
5. Signs of acute respiratory deterioration develop, as evidenced by a clinically significant increase in respiratory rate or effort (work of breathing) plus at least one of the following:
 - a) A persistent (at least 10 minutes) $\text{FiO}_2 \geq 0.70$ or sustained increase from baseline by ≥ 0.30 to maintain SpO_2 90% to 95%
 - b) A persistent (at least 5 minutes) transcutaneous $\text{PCO}_2 > 70 \text{ mmHg}$ or an increase from baseline by $\geq 20 \text{ mmHg}$
 - c) Recurring episodes of bradycardia
 - d) A sustained apneic event (≥ 20 seconds)

Subjects whose treatment is discontinued based on the PI's judgment will continue in the study. Subjects whose treatment is discontinued based on the parent/guardian's withdrawal of consent will be withdrawn from the study and no further data collection will be done.

Statistical Analysis The statistical analysis of objectives will be based on all enrolled preterm neonates. The subjects enrolled open-label with active treatment (the first 2 subjects from each site) will be summarized separately; however, AEs and other safety information may also be pooled with data from the double-blind portion of the study.

For the efficacy analysis, populations of all randomized subjects who received any treatment (modified intent-to-treat [mITT]) and subjects with no major protocol deviations or treatment interruptions (per-protocol) will be evaluated, based upon the treatment group to which they were randomized. For the safety analysis, all subjects randomized to the control group or who received any lucinactant for inhalation (including partial doses) will be evaluated, based upon the treatment they actually received.

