13.2 Statistical and Analytical Plans

The statistical analysis of both the primary and secondary objectives will be based on all enrolled preterm neonates who received study therapy. The first 2 subjects at each site, which were treated with open-label active therapy will be summarized separately. However, the safety data from these subjects may be pooled with the safety data from the subjects that received blinded therapy. The efficacy data will not be pooled.

For the efficacy analysis, all randomized subjects who received study therapy (modified intent-to-treat [mITT]) and subjects with no major protocol deviations (per-protocol) will be evaluated, based upon the treatment group to which they were randomized. If necessary, a population of subjects without treatment interruptions will also be defined and analyzed. For the safety analysis, all control subjects and subjects who received any amount of aerosolized lucinactant will be evaluated, based upon the treatment they actually received. All analyses will be performed for all subjects combined by treatment group and by gestational age strata.

All continuous variables (eg, weight, body temperature) will be summarized using number (n), mean, standard deviation (SD), median, 1st quartile, 3rd quartile, minimum, and maximum. All discrete variables (eg, sex, AEs, common complications of prematurity), will be summarized using frequency (n) and percent. Sites will be pooled for statistical analyses by geographic region.

The primary endpoint (the incidence of respiratory failure due to RDS or death within 28 days of life) is defined in Section 4.3.1. Respiratory failure due to RDS is defined as intubation (including intratracheal catheter placement) for MV and/or surfactant administration and will be compared between active treatment and control using the Cochran-Mantel-Haenszel (CMH) test, controlling for pooled sites.

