Exposure, defined as the emitted dose, is the amount of lucinactant that is delivered at the connection to the patient interface by the ADS at a constant rate of flow. The theoretical inhaled dose – the fraction of the aerosolized lucinactant that the infant is exposed to that is likely to be inhaled – is estimated by product of: 1) the aerosol concentration, 2) the minute ventilation of the infant, and 3) the administration time of the aerosol.

The first 2 infants enrolled at each site will receive open-label active treatment (lucinactant for inhalation); all subsequent infants will be randomized into the two masked treatment groups.

Treatment Group	Study Assignment
Lucinactant	Lucinactant for inhalation 160 mg TPL/kg (administered over 100 minutes) in conjunction with nCPAP (n = up to 35) Up to 3 repeat doses of 80 mg TPL/kg are to be given if repeat dosing criteria are met.
Control	nCPAP alone (sham treatment) for 110 minutes (n = up to 35) Up to 3 repeat sham treatments of 50 minutes are to be given if repeat dosing criteria are met.

Note: Masking procedures will be followed for all doses (initial and repeat).

Due to business considerations (and not as a result of safety concerns), enrollment for the study was terminated early on December 10, 2020. The last subject was enrolled on 27 November, 2020

and the last visit is expected on 19 January, 2021. A total of 12 subjects were enrolled. As a result, the planned analyses will be significantly curtailed and no statistical testing will be performed.

The independent data monitoring committee (DMC) was to evaluate the degree of risk involved in study participation and oversee the safety and welfare of study subjects. During the primary phase (all subjects have not yet completed 36 weeks PMA), the chair received regular reports on SAEs and AEs. The DMC was to have conducted 1 preplanned meeting after approximately 33% of subjects have been enrolled, which was cancelled.

Repeat dosing will be allowed up to 36 hours following randomization. Subjects meeting the repeat dosing criterion will receive up to 3 additional treatments of either 80 mg TPL/kg or sham treatment. The control subjects that meet the repeat dosing criteria must carry out all the procedures conducted for the active subjects to protect study blinding.

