1.2.1 Efficacy Objective

The primary estimand for this study is the occurrence of intubation for the purpose of mechanical ventilation or surfactant administration in preterm neonates 26 to 32 weeks PMA in the intent-to-treat (ITT) population (all randomized subjects). Intercurrent events include 1) treatment administration interruptions and 2) intubations for reasons other than MV or surfactant administration. Due to the small number of subjects as a result of the termination of the study, and that statistical testing will not be performed, intercurrent events will not be evaluated.

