Preterm neonates who successfully meet all eligibility criteria will be randomly assigned within their applicable stratum (26 to 28 completed weeks PMA or 29 to 32 completed weeks PMA) to one of the 2 treatment groups in a 1:1 ratio, following the first two open-label subjects at each site. Subjects will be randomized/enrolled using centralized allocation electronically (eg, interactive response technology [IRT]), including the open-label subjects (the first 2 subjects at each site). Neonates from multiple births will be randomized independently. Randomization information will be provided to the study drug preparer (eg, pharmacist). The PI, study staff (eg, site coordinator) (as applicable), and attending physicians as appropriate will be masked to the treatment assignment, as described in the site's blinding/masking plan. Infants who are randomized and on study nCPAP but no longer meet qualification criteria before treatment will still receive the study treatment, unless it is unsafe to do so in the opinion of the investigator.

If at any point during the delivery of lucinactant for inhalation a potential safety risk to the subject is identified, aerosolization must be discontinued and local NICU procedures followed to ensure the safety of the subject. Any significant clinical findings or observations must be documented and communicated to Windtree at the earliest time point possible.

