8 STATISTICAL TECHNICAL ISSUES

8.1 Methods of Assigning Subjects to Treatment Groups

Subjects will be assigned to receive either 160 mg TPL/kg lucinactant for inhalation in conjunction with nCPAP or control (sham treatment). Preterm neonates who successfully meet all eligibility criteria will be randomly assigned within their applicable stratum (26 to 28 completed weeks PMA or 29 to 32 completed weeks PMA) to one of the 2 treatment groups in a 1:1 ratio. Subjects will be randomized/enrolled using centralized allocation electronically (eg, interactive response technology [IRT]), including the open-label subjects (the first 2 subjects at each site). Neonates from multiple births will be randomized independently. Randomization information will be provided to the study drug preparer (eg, pharmacist). The PI, study staff (eg, site coordinator) (as applicable), and attending physicians as appropriate will be masked to the treatment assignment, as described in the site's blinding/masking plan. Infants who are randomized and on study nCPAP but no longer meet qualification criteria before treatment will still receive the study treatment, unless it is unsafe to do so in the opinion of the investigator.

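### SAP 4.1 merges the non-randomised open-label active infants into the ITT efficacy comparison, reversing the protocol's rule against pooling them

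*SAP*

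**What the plan says.** **Protocol.** The synopsis (section 1.1, Statistical Analysis) says: "The subjects enrolled open-label with active treatment (the first 2 subjects from each site) will be summarized separately". It allows pooling with the masked infants for adverse events and other safety data. Section 13.2 repeats both points and adds: "The efficacy data will not be pooled".

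**SAP on the open-label infants.** Section 4.1 says: "The subjects enrolled open-label with active treatment (the first 2 subjects from each site) will not be summarized separately". Its next sentence bases the primary and secondary objectives on all enrolled neonates, labelled ITT.

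**SAP on who is randomised and what ITT means.**
- Section 1.2.1 places the estimand in the "intent-to-treat (ITT) population (all randomized subjects").
- The Executive Summary gives the first two infants at each site open-label active treatment, after which "all subsequent infants will be randomized into the two masked treatment groups".
- Section 2.2.1 assigns infants "to one of the 2 treatment groups in a 1:1 ratio, following the first two open-label subjects at each site".
- Section 4.1 itself says that "subjects will be summarized according to their assigned (randomized) treatment".
- The Executive Summary (Analysis Populations) uses one population for efficacy and safety, namely all enrolled and treated infants. It justifies the ITT label on the ground that every randomised subject was treated.
- Sections 2.2.1 and 8.1 say that subjects are randomised or enrolled through the central system, "including the open-label subjects (the first 2 subjects at each site").

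**The concern.** The SAP reverses an explicit protocol rule without acknowledging it. The result is an active group made up of two kinds of infant: those allocated at random and masked, and those assigned to active treatment because they were among the first two at their site. The control group has only the first kind. A difference between such groups is not a randomised comparison, and calling it ITT tells the reader that it is.

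Two features make this more than a matter of labels. The primary endpoint turns on a clinician's decision to intubate, and protocol section 3.1 exempts the open-label infants from masking of the investigator. They are also the infants used to check that the device works and to rehearse procedures (protocol section 1.1, Study Design). Knowledge of treatment could delay intubation, while inexperience with the device could worsen outcomes, so the direction of any bias cannot be predicted.

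At stake is the descriptive treatment difference, the main efficacy result left after early termination. SAP 1.2 says the efficacy estimate will be used to size future studies. SAP 2.2.3 and 4.2 offer the difference both for planning and as support for efficacy.

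**Working it through.** **Step 1. Do the open-label infants enter the efficacy summaries as active?** Read alone, not summarising them separately could mean leaving them out. The rest of the SAP excludes that reading. Section 4.1 goes on to use all enrolled neonates, and the Executive Summary makes the efficacy and safety populations identical and defines only two groups, active and sham. The table list in section 11 has ITT efficacy tables but none for open-label or randomised-only infants. They can only be in the active column.

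**Step 2. Are they randomised subjects?** The central-system wording in sections 2.2.1 and 8.1 covers them. But their treatment is fixed as active, and both the Executive Summary and section 2.2.1 put the 1:1 allocation after them. Registration to a fixed assignment is not random allocation. They have no randomised treatment by which section 4.1 could group them.

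**Step 3. How much of the active group could they be?** The plan gives no figure to reproduce.

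Inputs:
- 12 infants enrolled, all in Poland (SAP 2.1).
- Two open-label infants per site, then 1:1 (SAP 2.2.1).
- Number of enrolling sites, k: not given, so varied from 1 to 6.

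Assumptions: the 12 include the open-label infants, each site enrolled at least two, and the remainder split evenly.

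Formulas:
- Open-label infants = 2k; randomised = 12 − 2k, or 6 − k per arm.
- Active group as the SAP forms it = 2k + (6 − k) = 6 + k.
- Open-label share w = 2k / (6 + k).
- Shift in the difference = w × gap, where gap is the event rate in open-label minus randomised active infants.

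| Sites k | SAP comparison | Randomised only | Share w | Shift per 10-point gap |
|---|---|---|---|---|
| 1 | 7 v 5 | 5 v 5 | 2/7 = 29% | 2.9 points |
| 2 | 8 v 4 | 4 v 4 | 4/8 = 50% | 5.0 points |
| 3 | 9 v 3 | 3 v 3 | 6/9 = 67% | 6.7 points |
| 4 | 10 v 2 | 2 v 2 | 8/10 = 80% | 8.0 points |
| 5 | 11 v 1 | 1 v 1 | 10/11 = 91% | 9.1 points |
| 6 | 12 v 0 | none | 12/12 = 100% | no control group |

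Sensitivity to the assumptions:
- A split one infant away from even gives shares of 25–33% (2/8 to 2/6), 44–57% (4/9 to 4/7), 60–75% (6/10 to 6/8) and 73–89% (8/11 to 8/9) for one to four sites.
- If one of two sites enrolled a single infant, there are 3 open-label and 9 randomised infants, and the share is 3/8 = 38% or 3/7 = 43%.

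**Step 4. What precision is lost by using randomised infants only?** The standard error is sqrt[0.44 × 0.56 × (1/nA + 1/nC)]. The 44% event rate in both arms is an assumption. It is the rate reported for all three groups of Study 03-CL-1202 (protocol 2.3.2.3), whose primary outcome was measured at 72 hours, not 28 days.

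| Sites k | SE, SAP comparison | SE, randomised only |
|---|---|---|
| 1 | 0.29 | 0.31 |
| 2 | 0.30 | 0.35 |
| 3 | 0.33 | 0.41 |
| 4 | 0.38 | 0.50 |

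**The case against.** **Early termination explains the change.** The Executive Summary ties the use of a single population to termination and says that the planned analyses will be cut back. This is a general reason for having one population. It does not mention or justify dropping the rule against pooling efficacy data, and a small sample does not make non-randomised infants comparable.

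**The SAP has two ITT definitions, and section 4.1 follows one of them.** True: the Executive Summary's version is all enrolled and treated infants. But its justification, that all randomised subjects were treated, does not reach infants who were never randomised. The inconsistency is part of the problem.

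**The protocol's wording is loose too.** It also refers to all enrolled neonates, and protocol 6.5 has the same central-system sentence. This stands, but section 13.2 settles the efficacy question explicitly.

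**Blinding procedures were still followed for the open-label infants.** Protocol section 6 requires this, to test each site's blinding plan. It does not mask an assignment that the investigator already knows.

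**The size is unknown and the consequence small.** This stands in part. Site count, split and event-rate gap are all missing, and no test is planned (SAP 1.3, 4, 8.3). With standard errors of about 0.3 to 0.5, neither version of the difference would be precise. That limits the harm to labelling and to a descriptive estimate, but the SAP itself proposes to use that estimate.

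**Conclusion.** The concern holds. SAP 4.1 contradicts protocol 13.2 and the synopsis, and it conflicts with the SAP's own account of who is randomised. As written, the SAP would report under the ITT label a difference in which non-randomised infants, whose treatment the investigator knows, are added to the active side only.

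The size of the distortion cannot be determined from the documents. Under the stated assumptions the open-label share of the active group is 29% to 91% for one to five sites, and each 10 points of event-rate gap shifts the difference by 2.9 to 9.1 points. The direction is unknown. With six sites there would be no control infant and no difference to report.

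No hypothesis test or error rate is affected, and pooling for safety is permitted by the protocol. This should be fixed, with high confidence in the contradiction itself.

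**What to change.** Bring SAP 4.1 back into line with protocol 13.2:

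- Give the open-label infants their own column in every efficacy table, and pool them for safety only.
- Compute treatment differences from randomised, masked infants only. If there are too few or none, say so and report counts without a difference.
- Use one meaning of ITT, all randomised subjects, in the Executive Summary and in sections 1.2.1 and 4.1.
- State in sections 2.2.1 and 8.1 that registering open-label infants in the central system is not randomisation. This also settles how to read the same sentence in protocol 6.5.
- Report the number of enrolling sites and the counts of open-label, randomised active and control infants.
- If an all-enrolled figure is still wanted, label it supplementary and non-randomised, and record it as a change from the protocol with a reason.

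The cost is wording, one table column and some precision. At the assumed 44% rate, the standard error rises only from 0.29 to 0.31 with one site, but from 0.38 to 0.50 with four. With five sites the randomised comparison is 1 v 1 and only counts are worth giving.
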